A crucial weakness of existing empirical studies comes from the operationalization of alcohol harm. With few exceptions,¹³ a vast majority of studies used a composite endpoint combining several causes of alcohol-attributable deaths or hospitalizations or even merging alcohol-attributable hospital admissions with deaths in a single outcome.^{6,9} While this strategy increases the statistical power to analyse rare events, composite endpoints are prone to misclassification bias by masking divergent underlying patterns and associations.¹⁴

Cause-specific analyses might shed light on different mechanisms driving the socioeconomic differences in overall alcohol-attributable harm, as well as opening potential avenues for policy interventions to reduce them. We will take advantage of a recently formed dataset covering the total Finnish population to explore associations between socioeconomic status and cause-specific alcohol-attributable events. An additional contribution to the literature will be reporting both relative and absolute inequalities in alcohol-attributable harm. Absolute differences have been rarely reported^{8,15} even though might be as relevant as relative differences because, from a pragmatic standpoint, they are more feasible to reduce.¹⁶

The study will aim to (1) examine the relative and absolute socioeconomic differences in cause-specific alcohol-attributable hospital admissions and deaths; (2) describe the geographical differences in cause-specific alcohol-attributable hospital admissions and deaths; and (3) quantify the relative contribution of each specific alcohol-attributable cause to the overall alcohol-attributable harm.

Methods

Study design and setting

The study is a nationwide population cohort study of the entire Finnish population from January 1, 2016, to 28 February 2020. Individuals in Finland are assigned a unique identifier at birth or immigration and used in all public and private administrative records. We will use the unique identifier to link socioeconomic information with hospital admissions and deaths.

Participants

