Participants will be all permanent residents (see below for a definition) aged 25 and over in Finland by the last day of 2015 and without an alcohol-attributable hospital admission during the past three years (January 2013-December 2015). The age limit of 25 was considered because younger adults might have their education ongoing and their income and occupational class may not reflect their true socioeconomic standing. We will exclude residents with prior hospital admissions during the past three years to reduce the risk of reverse causality.

Data sources

We will use data from the FOLK database (basic module, module for Household Dwelling Unit and module of Degree/Qualifications) maintained by Statistic Finland.¹⁷ The FOLK database contains individual-level data on income, education, family, degrees and qualifications and cohabitation. Educational level data comes from the Register of Completed Education and Degrees. Income data derive from Statistics Finland's income distribution statistics and personal taxation data. Occupation data derives from a combination of sources from registers of employment relationships, statistics on wages and salaries and data on enterprises.¹⁸ We will use data on hospital admissions from the Finnish Care Register for Health Care (HILMO) which covers all hospital admissions in public and private inpatient hospitals in Finland. We will use mortality data from the Causes of Death register administered by Statistics Finland.

Outcomes

The outcome will be cause-specific alcohol-attributable hospital admissions and deaths. We will include any wholly-attributable cause (i.e. an attributable fraction of 1) included in the main and secondary causes of hospitalization as well as the underlying and contributory causes of death. Drawing on national reports and previous studies,¹⁹ we will use the following International Classification of Disease (ICD) codes:

ICD-10 code	Diagnosis
F10.0-1	Alcohol intoxication
F10.2	Alcohol dependence
F10.3-9	Psycho-organic syndrome caused by alcohol
K70	Alcoholic liver disease
K85.2, K86.0	Pancreatic diseases caused by alcohol
K29.2	Gastritis caused by alcohol
I42.6	Alcoholic cardiomyopathy
G312, G4051, G621, G721	Degeneration of the nervous system due to alcohol, Epileptic seizures related to alcohol, Alcoholic polyneuropathy, Alcoholic myopathy
T51, X45	Alcohol poisoning

We will exclude perinatal causes (O354, P043, Q860) as they are impossible in this study population.

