Hospital admissions. We will define hospital admission as any event including at least one overnight stay in inpatient care. Patients having two hospital admissions in two hospitals with overlapping dates will be considered as a single hospital admission. We will include admissions where the main or secondary causes are attributable to alcohol. Given we are examining cause-specific alcohol-attributable events, we defined criteria to attribute the cause in case of overlapping or multiple alcohol-attributable ICD-10 codes. For hospital admissions with more than one alcohol-attributable cause, we will consider the main cause as the hospitalization cause. In hospital admissions with more than one alcohol-attributable ICD-10 code, we will consider the main cause as the hospitalization cause. If there are several alcohol-attributable main causes, we will consider first the complexity of the inpatient provider (provider code in the HILMO dataset). In the case of ties by complexity, we will consider the longest stay. We will not include outpatient visits, day-hospital treatments or emergency care visits.

Deaths. We will define alcohol-attributable deaths as any death where an alcohol-attributable cause is either the underlying, immediate, intermediate or contributory cause of death.

We will follow participants until the first hospital admission, death or end of follow-up. We will restrict follow-up until February 28, 2020, to avoid confounding due to the COVID-19 pandemic.

Exposure

The exposure of interest is socioeconomic status. Our main proxy of socioeconomic status will be disposable household income. In addition, we will use educational level and occupational class. All exposures are measured by the last day of the calendar year (2015). We will calculate equivalised disposable income by adjusting the combined disposable income of a household to the household size unit using the OECD-modified equivalence scale. The income measure in this study is the sum of wage and salary earnings, self-employment income, property income and current State transfers after subtracting direct taxes and social security contributions. For persons in non-dwelling units (e.g. living in institutions, homeless, abroad or registered as unknown) we will consider their personal net income without equalization. We will also run sensitivity analyses excluding those participants.²⁰

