The use of administrative records does not require ethical approval in Finland. All data used was pseudonymised and linked by Statistics Finland and will be analysed in a protected remote access system FIONA. We will comply with Finnish regulations established under the National Statistics Act and the supplementary National Data Protection Act as well as with the General Data Protection Regulation from the European Union.²⁵ Permission for data usage and linkage was given to the Finnish Institute for Health

and Welfare as part of the Compensation Criteria and Evaluation of Provinces project (permission K/3184/07.03.00/2022, U1098_a19)

Statistical methods

We will use the relative index of inequality (RII) and the slope index of inequality (SII) to compare and quantify the socioeconomic gradient in cause-specific alcohol-attributable hospital admissions and deaths. We will use regression models for estimation with individual time-to-event data: Cox proportional hazards models for relative inequalities and Aalen additive hazard models for absolute inequalities.

For the RII, we will fit the following Cox proportional hazards model,

$$(1) \quad \lambda(t | G = k) = \beta_0(t) \exp\{\beta x_{(k)} + \beta(t)L_i\}$$

Where G represents the socioeconomic group and we approximate the rank of each person in the k th socioeconomic group by the rank $x_{(k)}$ defined as the percentage of the population in strictly higher groups plus half of the percentage in group k , and L_i denotes a vector of covariates (sex, marital status, etc.).²⁶ This method allows us to incorporate the whole socioeconomic gradient, instead of comparing the lowest and highest socioeconomic groups. The estimate of \widehat{RII} is equivalent to $\exp(\widehat{\beta})$.²⁶

We will use age as the timescale, as age is strongly correlated with the risk of hospitalization and mortality.²⁷ We will report regression estimates as hazard ratios (HRs) with 95% confidence intervals (CIs). Given we studied cause-specific events, deaths due to other causes represent competing risks. To account for this, we will use cause-specific hazards by censoring other-cause events to the time of the death by other causes or the end of follow-up on February 28, 2020. We will examine the proportional hazards assumption globally and for each covariate using scaled Schoenfeld residuals.²⁸

For the SII, we will fit age-standardized Aalen additive hazard models,

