$$(2) \quad \lambda(t | G = k) = \alpha_{0s}(t) + \alpha_s x_{s(k)} + \alpha(t)L_i$$

where the age standardization is the weighted sum of estimated age-group-specific indices. For this we will fit separate additive hazard models within each age-group $s = 1, \dots, S$. The estimate of the \widehat{SII} is equal to $\widehat{\alpha}$.

Same as before, we will use age as the timescale and report regression estimates as events per 100,000 person-years with 95% confidence intervals. We will report cause-specific hazards to account for competing risks.

In practice, we will run a model for each cause-specific condition (nine models in total) separately for alcohol-attributable hospital admissions and alcohol-attributable deaths.

For objective 2, we will run stratified analyses by hospital districts and Åland (n =21). We will report the RII and SII by region in plots or maps in order to obtain a visual representation of both the degree of between-region inequalities and geographical patterns in the distribution of alcohol-attributable harm. Considering we might not have enough statistical precision to obtain informative estimates for regional differences for all cause-specific outcomes, we will report overall alcohol-attributable admissions and deaths (separately) and, in the Supplementary Appendix, the most common specific causes.

For objective 3, we will quantify the relative contribution of each specific cause by dividing the SII for the specific cause by the overall SII for either hospital admission or death and multiplying by 100.

We will run the same Cox proportional hazards and additive hazards models for educational level and occupational class. However, given these are categorical variables with an unclear ordinality and the relationship with the outcome might not be linear, we are not able to estimate the RII or SII. Instead, we will use the standard approach of comparing the hazard ratio and additive hazard comparing the category to a reference group (highest education and upper-level employees, respectively).

Missing data for covariates in the FOLK datasets is minimal. Sex, age, marital status and mother tongue do not have missing data. We described above how we will handle missing data for education. For models using income and occupation, we will use multiple imputation using chained equations to address missing data.

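### Objective 2 asks how alcohol-attributable admissions and deaths differ between regions, but the only regional measures named, the RII and SII, describe the income gradient and do not directly show a region's level of harm

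*Combined protocol and SAP*

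**What the plan says.** The aims paragraph just before Methods lists three objectives. The first is expressly about socioeconomic differences. The second is to "describe the geographical differences in cause-specific alcohol-attributable hospital admissions and deaths", with no mention of socioeconomic status.

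Statistical methods introduces the RII and SII as the means "to compare and quantify the socioeconomic gradient in cause-specific alcohol-attributable hospital admissions and deaths". Each is the coefficient on a socioeconomic rank (for the RII, its exponential), from a Cox model and an additive hazards model respectively. The section adds that neither index can be estimated for education or occupation, so in practice both are indices of income.

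For objective 2 the same section stratifies the analysis by hospital district and Åland, 21 areas in all, and states: "We will report the RII and SII by region in plots or maps". The maps are meant to show two things: how large the inequalities between regions are, and "geographical patterns in the distribution of alcohol-attributable harm". The next sentence notes that precision may be too low for every specific cause. It limits the regional reporting to overall admissions and overall deaths, taken separately, with the commonest causes in the appendix. It names no measure.

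**The concern.** An objective about where admissions and deaths are more or less frequent needs a measure of frequency by area. The two indices named measure something else: how unequally the events fall across income inside each area. Of the two things the maps are said to show, regional variation in inequality is within their reach. The geographical pattern of harm is not directly shown, unless that phrase means the distribution of harm across income. In that case the objective as stated in the aims is wider than the analysis.

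At stake is how the regional results are read. If the plan is followed as written, a map of income gradients may be taken for a map of where alcohol harm is concentrated, and one of the three stated aims would have no direct measure of its target.

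**Working it through.** **Regional figures in the plan.** There are none to reproduce: the documents give no regional rate, event count, RII or SII. The check has two parts, what the indices contain and a numerical illustration with assumed inputs.

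**What the indices contain.** Take a linear hazard in one region, rate(x) = a + s·x. Here x is the income rank defined in Statistical methods, expressed as a proportion from 0 (highest income) to 1 (lowest), and formed within the region so that its mean is 0.5. Then:

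- RII = (a + s)/a
- SII = s
- mean regional rate = a + s/2
- hence SII = mean rate × 2(RII − 1)/(RII + 1)

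The level of harm cancels out of the RII. For example, a = 100, s = 300 and a = 200, s = 600 both give RII 4, while the mean rates are 100 + 150 = 250 and 200 + 300 = 500. The SII is the level multiplied by a function of the gradient, so it does not identify the level by itself. With flat gradients, regions at 100 and at 500 both have RII 1 and SII 0, and a five-fold difference does not appear on either map.

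**Illustration of reversed order** (rates per 100,000 person-years; rates and RIIs are assumed).

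| Region | Mean rate | RII | 2(RII − 1)/(RII + 1) | SII |
|---|---|---|---|---|
| A | 300 | 1.25 | 0.50/2.25 = 0.222 | 300 × 0.222 = 67 |
| B | 100 | 3 | 4/4 = 1.000 | 100 × 1.000 = 100 |

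Region A has three times the rate of region B, yet it is lower on the RII map (1.25 against 3) and on the SII map (67 against 100).

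**Does this example depend on the model form or the ranking?** With a log-linear hazard over ten equal deciles, and the SII taken as the least-squares slope, the two SIIs are 67 and 108. The Supplementary Appendix sets income decile limits on the whole population aged 25 or older, and the plan does not say whether ranks are re-formed within each area. With national ranks and a regional mean rank m, SII = rate × (RII − 1)/(1 + (RII − 1)m). For an assumed m of 0.4 to 0.6:

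- Region A: 300 × 0.25/1.10 = 68 down to 300 × 0.25/1.15 = 65
- Region B: 100 × 2/1.8 = 111 down to 100 × 2/2.2 = 91

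The reversal holds in this example throughout. All of these are unadjusted sketches; the planned models also adjust for covariates and standardise the SII for age.

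**The case against.** **The objective may simply be loosely worded.** This is the strongest reply. Objective 3 also omits socioeconomic status in the aims, since it asks for each cause's share of overall alcohol harm, yet Statistical methods answers it with a ratio of SIIs. The title given in the Supplementary Appendix is about socioeconomic differences in harm, and the objective 2 text speaks of inequalities between regions. In this protocol harm may well be shorthand for inequality in harm. This stands as a plausible account of the intention. It does not remove the mismatch, but it means that a change of wording may be all that is needed.

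**The sentence on overall admissions and deaths might promise regional totals.** It is introduced by a remark on insufficient precision for cause-specific regional estimates, so it reads most naturally as a choice of outcomes for the RII and SII. On the looser reading it still names no measure.

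**The SII is absolute, and with the RII it implies a level.** Under a linear gradient, mean rate = SII × (RII + 1)/(2(RII − 1)). But the two indices come from separate covariate-adjusted models, and the result is unstable near RII 1: with SII 10, RII 1.05 gives 10 × 2.05/0.10 = 205, and RII 1.10 gives 10 × 2.10/0.20 = 105. This is not direct reporting of a level.

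**Stronger readings that a reader might infer.** One is that the maps will put regions in the wrong order of harm. The documents hold no regional figures, so they cannot show this; the illustration only shows that it can happen. Another is a simple rule, that the order is wrong only where the lower-rate region has the larger RII. The documents do not support that either, because the ranking is not settled. With national ranks, 110 per 100,000 at RII 3.2 and mean rank 0.6 gives SII 110 × 2.2/2.32 = 104, below 111 for 100 at RII 3 and mean rank 0.4, although the higher-rate region has the larger RII.

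**Conclusion.** The point holds as a mismatch between an objective and its stated analysis. As worded, objective 2 concerns regional differences in admissions and deaths; the only regional measures named describe the income gradient; and no regional measure of level is specified anywhere in the documents. That part rests on the text alone and needs no assumption.

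The practical size cannot be given. The reversal shown above rests on assumed rates and RIIs and establishes possibility only. The scope is limited to this descriptive objective: the national RII and SII, the cause-specific models and the analysis of objective 3 are untouched. Whether the study team meant levels or inequality is open, and the protocol should settle it before the maps are made.

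**What to change.** Choose one of two changes.

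(a) **If regional levels are wanted.** For the 21 areas, add age- and sex-standardised rates per 100,000 person-years with 95% confidence intervals, for overall alcohol-attributable admissions and deaths separately, and put the most common causes in the appendix. Label them as rates in a cohort "without an alcohol-attributable hospital admission during the past three years" (January 2013 to December 2015). For admissions, label them also as first-event rates, since the plan says "We will follow participants until the first hospital admission, death or end of follow-up". They are not a region's total burden. Label the RII and SII maps as regional variation in income inequality. The cost is one further tabulation of events and person-years from data already linked, and one more table or map per outcome.

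(b) **If only regional inequality was intended.** Restate objective 2, and the sentence in Statistical methods on what the maps show, as regional differences in socioeconomic inequality in alcohol-attributable harm. The cost is wording only.

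Under either option, name the measure in the sentence on regional reporting of overall admissions and deaths.

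### Objective 2 judges how far regions differ by eye from 21 separately fitted RIIs and SIIs, and the plan never estimates how much of that spread exceeds sampling error

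*Combined protocol and SAP*

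**What the plan says.** The aims in the introduction make the second objective descriptive: to "describe the geographical differences in cause-specific alcohol-attributable hospital admissions and deaths". Its method is one paragraph of the Statistical methods section.

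- **Analysis:** "we will run stratified analyses by hospital districts and Åland (n =21").
- **Display:** "We will report the RII and SII by region in plots or maps". The stated purpose is to let the reader see two things: how unequal the regions are, and the geographical pattern ("in order to obtain a visual representation of both the degree of between-region inequalities and geographical patterns").
- **Precision:** the plan concedes that "we might not have enough statistical precision to obtain informative estimates for regional differences for all cause-specific outcomes". Its response is that "we will report overall alcohol-attributable admissions and deaths (separately") by region, with the most common specific causes in the Supplementary Appendix.

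Intervals are promised earlier in the same section for the Cox models ("We will report regression estimates as hazard ratios (HRs) with 95% confidence intervals (CIs")) and, in similar words, for the additive models. Neither statement is specific to the regional displays.

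The documents name no heterogeneity test, region-by-income interaction, between-region variance, multilevel or random-effects model, smoothing, or minimum event count for showing a region.

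**The concern.** When a model is fitted separately in each of 21 regions, the variance of the estimates across regions is the true between-region variance plus the average sampling variance. A reader who judges the degree of regional inequality from the spread of plotted or mapped values sees the sum. The spread is therefore biased upwards, and most strongly where events are few. If regions differ in size, the most extreme values also tend to come from the small ones, so part of an apparent geographical pattern may only reflect where the small regions lie.

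At stake is the interpretation of objective 2. The quantity that the display is meant to convey is never estimated, so a report could describe marked regional contrasts that are mostly sampling error. It could equally fail to say that the regions are compatible with a common gradient.

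**Working it through.** The documents give no event counts, region sizes or power figures, so there is no figure of the plan's to reproduce. What follows is an illustration for the RII under stated assumptions.

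**Inputs from the documents**
- 21 regions (Statistical methods, objective 2).
- Income in deciles, each given its midpoint rank (Statistical methods; Supplementary Appendix, Income). For equal deciles the ranks are 0.05, 0.15, ..., 0.95, with variance 0.0825 and SD √0.0825 = 0.287.

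**Assumed**
- The number of events D in each region.
- Identical true RII in all regions.
- The approximation SE(log RII) = 1/(0.287 × √D). It ignores covariate adjustment and departures of a region's income distribution from the national deciles.

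**Equal events per region.** The median range of 21 independent standard normal values is about 3.73 (by simulation). The median ratio of largest to smallest RII from noise alone is therefore about exp(3.73 × SE).

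| Events per region | SE(log RII) | Median max/min RII, no true variation |
|---|---|---|
| 50 | 0.492 | 6.3 |
| 100 | 0.348 | 3.7 |
| 200 | 0.246 | 2.5 |
| 500 | 0.156 | 1.8 |
| 1,000 | 0.110 | 1.5 |

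For a single region with 20 deaths, SE = 1/(0.287 × √20) = 0.78. The 95% CI then extends by a factor exp(1.96 × 0.78) ≈ 4.6 either way.

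**Unequal regions.** For this step the common true RII was set at 3. The hazard-weighted rank variance is then 0.0777 instead of 0.0825, which changes the SE by about 3%. Region sizes were spaced geometrically, and each setting used 20,000 simulated sets of 21 estimates.

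| Total events | Equal regions | Size ratio 10 | Size ratio 30 | Size ratio 60 |
|---|---|---|---|---|
| 2,000 | 3.9 | 6.2 | 11.5 | 20.4 |
| 5,000 | 2.4 | 3.2 | 4.7 | 6.7 |
| 10,000 | 1.9 | 2.3 | 3.0 | 3.9 |
| 30,000 | 1.4 | 1.6 | 1.9 | 2.2 |

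Entries are again the median max/min ratio with no true variation. The highest RII falls in the smallest third of regions in about 68% of runs at a size ratio of 10, 78% at 30 and 82% at 60. With equal regions the figure is 33%, as chance requires.

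**Do regional CIs settle it?** If all 21 regions share one true RII, the chance that at least one 95% CI excludes it is 1 − 0.95²¹ = 0.66. CIs show how imprecise each region is, but they do not measure the variation between regions.

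**What a summary analysis would show** (size ratio 30; Cochran's Q on 20 df, critical value 31.4; DerSimonian-Laird estimate with empirical-Bayes shrinkage)

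| Total events | True SD of log RII | True max/min | Raw max/min | Shrunken max/min | Q rejects |
|---|---|---|---|---|---|
| 2,000 | 0 | 1.0 | 11.5 | 1.0 | 5% |
| 10,000 | 0 | 1.0 | 3.0 | 1.0 | 5% |
| 2,000 | 0.2 | 2.1 | 12.5 | 1.4 | 23% |
| 10,000 | 0.2 | 2.1 | 3.6 | 1.7 | 85% |
| 30,000 | 0.2 | 2.1 | 2.6 | 1.8 | about 100% |

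The raw spread overstates the true spread, and the shrunken spread understates it. Neither is a good measure of the degree of variation, which is why the between-region SD should be reported.

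No figure was worked out for the SII. Its models are fitted within age groups as well, so each region's events are divided further.

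**The case against.** The strongest case for the plan has four parts.

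1. **The plan sees the precision problem and acts on it.** Its concession is confined to cause-specific outcomes, and reporting overall admissions and deaths by region raises the events per region. This stands as mitigation. It lowers the noise without saying how much remains. A reader might infer that the plan admits its regional estimates to be uninformative in general. The full sentence does not support that.
2. **Uncertainty may well be shown.** The text says plots or maps, a plot can carry CIs, and the stratified models are runs of models for which 95% CIs are promised. It would be wrong to say that the plan shows bare point estimates or ignores uncertainty. What stands against the plan is narrower: CIs are not expressly promised on the regional displays, and 21 separate CIs do not estimate between-region variation.
3. **The objective is descriptive.** No regional test, ranking or decision is planned, so the plan does not commit itself to declaring that regions differ. That is correct, but a description of how much regions differ should still not be inflated by sampling error.
4. **The size cannot be established from the documents.** This also stands. A reader might infer from the larger ratios that the maps will be mostly noise, or that the extremes must be the smallest districts. The first depends on assumed low event counts. The second holds only if regions differ in size, which the documents do not report.

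**Conclusion.** The point holds as an omission in the analysis of objective 2. The plan sets out to show the degree of regional inequality but has no step that separates true variation from sampling error, so the visible spread overstates it.

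The amount depends on event counts and region sizes that the documents do not give. If events are many, as they may be for overall admissions, the excess may be small: a ratio of about 1.5 from noise alone at 1,000 events per region. It is likely to be larger for deaths and for the specific causes in the appendix, at about 3.7 with 100 events per region, and larger again if regions are unequal. These figures are illustrations for the RII only.

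The national RII and SII (objective 1) and the cause contributions (objective 3) are not affected. This is a worthwhile, inexpensive improvement to one descriptive objective and does not threaten the study's main results.

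**What to change.** Add to the objective 2 paragraph, for each outcome reported by region:

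- Combine the 21 log-RIIs, and separately the 21 SIIs, in a random-effects meta-analysis.
- Report the between-region SD with its 95% CI, together with a heterogeneity test, as the measure of how unequal the regions are.
- Show every regional estimate with its 95% CI in a forest plot beside any map.
- Optionally add a map of shrunken estimates as a supplement. State that it understates the true spread when events are few, and that this model pulls regions towards a common mean without using their location.

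The cost is a few lines of text and a second-stage analysis of estimates that the plan already produces. No new data are needed. The drawback is that an SD estimated from 21 regions may be imprecise, and the heterogeneity test has little power when events are few. The SD's CI should therefore be reported whatever the test shows, and a non-significant test should not be read as evidence that regions are alike.

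### Objective 3's cause shares need not sum to 100%: deaths have no single-cause rule, and it is unclear when follow-up ends in the admission models

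*Combined protocol and SAP*

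**What the plan says.** All places are in the combined protocol and SAP.

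- **Objective 3 (Statistical methods).** "we will quantify the relative contribution of each specific cause by dividing the SII for the specific cause by the overall SII". The measure is obtained by "dividing the SII for the specific cause by the overall SII for either hospital admission or death and multiplying by 100".
- **Models (Statistical methods).** "we will run a model for each cause-specific condition (nine models in total) separately for alcohol-attributable hospital admissions and alcohol-attributable deaths". The overall model, which supplies the denominator, has no specification of its own. The SII comes from additive hazard models fitted within age groups, "where the age standardization is the weighted sum of estimated age-group-specific indices".
- **Deaths (Outcomes).** An alcohol-attributable death is "any death where an alcohol-attributable cause is either the underlying, immediate, intermediate or contributory cause of death".
- **Admissions (Outcomes).** An admission with several alcohol codes goes to its main cause. If several main causes are alcohol-attributable, provider complexity decides, then length of stay. Admissions with alcohol only in a secondary position are also included.
- **Follow-up (Outcomes).** "We will follow participants until the first hospital admission, death or end of follow-up".
- **Competing risks (Statistical methods).** The models use cause-specific hazards, "censoring other-cause events to the time of the death by other causes or the end of follow-up on February 28, 2020".

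**The concern.** A cause's contribution to overall harm, given as a percentage of the overall index, will be read as part of a whole. That reading needs two conditions: each event belongs to one cause, and the cause models and the overall model follow the same people for the same time. The plan does not secure the first for deaths or the second for admissions.

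If either fails, a person or a death can enter several numerators and the denominator once. The percentages then overlap and do not divide up the overall gradient. The overlap need not inflate all causes equally, so it can distort comparisons between causes as well as the total.

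**Working it through.** **Inputs.** The plan states no contribution figure, event count or rate of multiple coding, so there is nothing to reproduce. The check is algebra plus simulation with assumed inputs.

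**1. When the shares add up.** Take the constant-effect additive hazard estimator with income rank x as the only covariate. For cause j:

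SII_j = [Σ_i ∫ (x_i − x̄(t)) dN_ij(t)] / [Σ_i ∫ (x_i − x̄(t))² Y_i(t) dt]

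Y_i is the at-risk indicator, N_ij counts events of cause j, and x̄(t) is the mean rank among those at risk. With a common Y, the denominator and x̄(t) are the same in every model. If each event has one cause, Σ_j N_ij = N_i, so Σ_j SII_j equals the overall SII exactly. Covariates turn the denominator into a matrix that all models still share. Summing over age groups with the same weights keeps the equality.

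**2. Deaths.** Death ends follow-up in every model, so the nine death models and the overall death model can share one risk set. Assignment is what fails. If death i lists m_i of the nine groups and enters each of them:

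sum of shares = 100 × Σ m_i (x_i − x̄) / Σ (x_i − x̄), summed over alcohol deaths.

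The sum exceeds 100% whenever the extra listings are themselves more frequent at lower income. If a proportion q lists exactly one second group, unrelated to income, the expected sum is 100 × (1 + q).

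The simulation assumed 400,000 people, 4.16 years, decile ranks, an alcohol-death hazard of 0.0008 × (0.4 + 2x) per year, and a second group drawn at random. It gave 1,794 alcohol deaths. Differences from 100 × (1 + q) are of the size that chance produces with that number.

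| q (assumed) | 100 × (1 + q) | Simulated, every listed group | Simulated, one group per death |
|---|---|---|---|
| 0% | 100% | 100.0% | 100.00% |
| 10% | 110% | 108.1% | 100.00% |
| 25% | 125% | 122.0% | 100.00% |
| 50% | 150% | 151.1% | 100.00% |

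**3. Admissions: assignment.** The main-cause hierarchy settles most multi-code admissions. It has nothing to act on when two or more alcohol codes are all secondary.

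**4. Admissions: risk set.** The follow-up rule stops at the first admission but does not say whether that means any alcohol cause or the modelled cause. The competing-risks sentence names only other-cause death and the end of follow-up. It is silent on an earlier admission for a different alcohol cause. The two readings were simulated with nine causes, 400,000 people, 4.16 years, and gamma frailty (variance 0, 20, 60 and 150) to make some people prone to several causes:

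| Admitted persons with two or more causes (assumed) | All models stop at first alcohol admission | Each model stops at its own cause only |
|---|---|---|
| 1.4% | 100.00% | 100.7% |
| 16.4% | 100.00% | 141.3% |
| 32.4% | 100.00% | 197.9% |
| 47.4% | 100.00% | 320.8% |

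A second simulation (relative index of inequality 5, 3 first events per 1,000 person-years) gave 111%, 123% and 142% when the hazard of the remaining causes rose 10-, 20- and 40-fold after a first alcohol admission. With shared frailty of variance 2 or 10 and no such rise, it gave 103% and 111%.

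Inflation is not uniform. In the 16.4% row, one cause goes from 8.1% to 13.3% (13.3 / 8.1 = 1.64) and another from 22.3% to 29.4% (29.4 / 22.3 = 1.32).

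The simulations use time on study, no covariates and one age stratum. The algebra in step 1 does not depend on those simplifications.

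**The case against.** The plan defines its percentage explicitly and never promises a total of 100%. Overlapping shares are a legitimate summary if labelled as such. That stands, but the plan does not label them, and objective 3 calls them contributions to overall harm.

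Several stronger readings are tempting, and the documents do not support them:

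- **That the plan assigns no event to a single cause.** Admissions have a hierarchy; the gap is admissions with only secondary alcohol codes. The statement holds for deaths.
- **That the models lack a common risk set.** This does not apply to deaths. For admissions, the follow-up rule can be read as stopping at the first alcohol admission of any cause. The shares are then exact once each admission has one cause.
- **That a person stays at risk after an admission for another alcohol cause.** The competing-risks sentence follows a remark about deaths from other causes. Its silence on earlier alcohol admissions is an ambiguity, not a stated rule.
- **That the simulated totals estimate the Finnish excess.** Every rate, gradient, multiplier and frailty variance is assumed. The plan also excludes people with an alcohol admission in the previous three years.
- **That the excess is largest for causes that tend to follow another alcohol admission.** No calculation here modelled cause-specific sequences.

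The additional analysis separating underlying from contributory causes helps only in part. It is not tied to objective 3 and does not allocate deaths in the main analysis.

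**Conclusion.** The point holds in limited form: the objective 3 shares are not guaranteed to sum to 100% and would generally exceed it. The deaths part is firm, because any-position counting without an assignment rule lets one death enter several numerators. The admissions part is an ambiguity in the stopping rule plus a small gap for admissions with only secondary codes.

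The size cannot be derived from the documents. Death shares sum to about 108% to 151% on the assumption that 10% to 50% of alcohol deaths list a second group, with second listings unrelated to income. For admissions the total is exactly 100% under one reading. Under the other it ran from just above 100% to several times that, depending wholly on assumed clustering of causes within persons. Because these percentages are all that objective 3 reports, the plan should be amended before analysis.

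**What to change.** For objective 3:

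1. **Deaths.** Follow to death or end of follow-up, so that deaths after an alcohol admission are kept. Assign each death to one group: the underlying cause if alcohol-attributable, otherwise a fixed order of the other certificate positions.
2. **Admissions.** End follow-up in all nine models and the overall model at the first alcohol-attributable admission of any cause. Add a fixed order for admissions whose alcohol codes are all secondary.
3. **Common specification.** Write out the overall model. Use the same ranks, covariates, age groups, weights and imputed data sets in it and in the cause models. The slopes then sum exactly to the overall SII.

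Per-cause first admissions and any-position deaths can stay for objective 1, with a sentence saying which follow-up rule serves which objective. If they are also reported as shares, label them as overlapping and not a decomposition.

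The cost is some wording and one extra set of additive hazard fits. The downside is that the objective 3 admission shares then describe first alcohol admissions only. Confidence intervals for the shares, from a bootstrap that resamples numerator and denominator together, are optional; in a total-population cohort with multiple imputation they would add noticeable computing time.
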